Bone mineral density will be evaluated in all patients at the lumbar spine (L1-L4), femoral neck, and total hip at the Week 24/Baseline, Week 36, and Week 52/Early Termination visits. The absolute, change, and percent change from parent study Baseline and Z-scores will be summarized by visit and parent study treatment group.

The mean percentage change at Week 52 from parent study Baseline in bone mineral density and corresponding 95% CI will be provided for each treatment group. For patients who were randomized to 24 weeks of treatment with relugolix and add-back in the parent studies (Group A in MVT-601-3001 or MVT-601-3002) and enrolled in the extension study, the lower bound of the 95% CI for mean percentage change at Week 52 from parent study Baseline in bone mineral density lumbar spine (L1-L4) will be compared with a pre-specified clinically acceptable threshold of -2.2% to evaluate magnitude of bone mineral density loss after 52 weeks of treatment. If the lower bound is > -2.2%, the relugolix add-back treatment arm will be considered to have successfully prevented bone mineral density loss.

Sample Size Estimation

Because this is an extension study, the sample size will be determined by the number of patients who have completed a parent study (MVT-601-3001 or MVT-601-3002) and who are eligible and willing to participate in the extension study. It is estimated that approximately 600 patients (75% of the total of 780 patients who will be randomized into the parent studies) will participate in this study.

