In summary, relugolix at a dose of 40 mg once daily resulted in a marked decrease in the heavy menstrual bleeding associated with uterine fibroids in a majority of women in a well-designed large phase 2 study. However, its administration was associated with a degree of bone mineral density loss unacceptable for long-term treatment. This phase 3 study extension study will assess long-term efficacy and safety of relugolix 40 mg co-administered with low-dose of estradiol and norethindrone acetate to decrease heavy menstrual bleeding associated with uterine fibroids and to prevent the bone mineral density loss and ameliorate some of the other side effects of a hypoestrogenic state such as hot flushes.

This open-label extension study will allow for a description of long-term efficacy data and safety for an additional 28 weeks of treatment, providing approximately 1 year of efficacy and safety data from the women originally randomized to relugolix in studies (MVT-601-3001 and MVT-601-3002). This study design will allow eligible patients with heavy menstrual bleeding associated with uterine fibroids, who were randomized to placebo in the parent study, to receive relugolix co-administered with low-dose hormonal add-back therapy during the extension.

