6.3. Early Termination Visit and Follow-up Visit

All patients withdrawing from the study prior to Week 52 will complete an Early Termination visit. The Early Termination visit procedures are identical to those of Week 52; however, for patients whose last dose of study drug is during Week 32 or earlier, the following procedures do not need to be performed: transvaginal ultrasound (with or without a transabdominal ultrasound), bone densitometry, and endometrial biopsy. These procedures may be performed at the investigator's discretion if they aid in follow-up of ongoing adverse events.

Patients (including those who complete the Week 52 visit and those who withdraw early from this study) will have a Follow-up visit approximately 30 days after the last dose of study drug, or prior to the date of initiation of another investigational agent or hormonal therapy affecting the hypothalamic-pituitary-gonadal axis or surgical intervention or other invasive procedure for uterine fibroids, whichever occurs first. However, for patients who enroll directly into another relugolix clinical study upon completion of the Week 52 visit, then the Follow-up visit may be waived.

The Follow-up visit will be used to assess safety after discontinuation of study treatment including adverse events, clinical safety laboratories, and return of menstruation. Refer to the Schedule of Activities (see Section 1.1) for individual study visit procedures during the Follow-up visit.

At an Early Termination visit occurring on or after Week 36, patients with a bone mineral density loss of > 3 relative to the parent study Baseline measurement will undergo a follow-up bone densitometry scan at 6 (± 1) months and will be contacted to question them about medications and conditions (eg, pregnancy) that might affect bone mineral density through the time of follow-up bone densitometry. If Early Termination occurs prior to Week 36, follow-up bone densitometry will be performed according to the requirements of the parent study. The follow-up bone densitometry will be submitted for central reading.

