7.10. Benefit/Risk Assessment

Adverse drug reactions (identified risks) associated with relugolix in women include nonserious events of hot flush, headache, hyperhidrosis, and loss of bone mineral density. In this protocol, relugolix will be evaluated for its benefit on the heavy menstrual bleeding associated with uterine fibroids. Low-dose hormonal add-back therapy with estradiol and norethindrone acetate will be evaluated for maintenance of bone mineral density during treatment with relugolix.

Potential risks that may be associated with relugolix treatment in women, based on nonclinical data and data available for similar compounds, include drug interactions, cardiovascular effects (corrected QT interval [QTc] prolongation), hepatic enzyme increases, phospholipidosis (PLD), reproductive toxicity, and metabolic and cardiovascular changes (insulin resistance, dyslipidemia, increased weight) with an increased risk of diabetes mellitus and possible increased risk of cardiovascular disease. Additionally, there are potential risks associated with

the addition of estradiol/norethindrone acetate. Summaries of findings from both nonclinical and clinical studies conducted with relugolix can be found in the current version of the investigator brochure.

The risk assessment and mitigation strategy for this protocol are outlined in [Table 6](#).

Table 6: Protocol Risk Assessment and Mitigation Strategies

Potential Risk of Clinical Significance	Mitigation Strategy	
	Impact on Eligibility	Monitoring and Withdrawal Criteria
Bone Mineral Density Reversible loss of bone mineral density is a risk of the hypoestrogenic state induced by relugolix. This risk is mitigated by the co-administration of low-dose estradiol and norethindrone acetate hormonal add-back therapy.	Exclusion criteria for a history of osteoporosis, metabolic bone disease, and prior medical therapy for low bone mineral density was included in the parent studies.	Bone mineral density will be monitored at the Week 24/Baseline, Week 36, and Week 52/Early Termination visits with specified discontinuation and follow-up criteria and all fractures will be reported as adverse events.
Drug Interactions	Exclusion of co-administration P-glycoprotein inhibitors/inducers.	Collection of adverse events.

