Clinical laboratory data consist of chemistry, hematology, and hormonal tests. Only data collected by the central laboratory will be used to do the analyses. ECGs will also be read centrally. The distributions of QTc interval will be summarized at each visit. All data will be listed and summarized by visit. The change from parent study Baseline to each post-baseline study visit will be presented by treatment group for each ECG parameter.

The incidence of vasomotor symptoms as assessed through adverse event reporting will be summarized by the parent study treatment arm.

Bone mineral density data will be collected and analyzed by the central radiology laboratory including bone mineral content (g), bone area (area, cm²), and bone mineral density (g/cm²) each for L1, L2, L3, L4, total hip, and femoral neck, and average bone mineral density of L1-L4 (lumbar spine), Z-score for bone mineral density lumbar spine (L1-L4), total hip, and femoral neck.

For the relugolix add-back treatment Group A, the lower bound of the 95% CI for (arithmetic) mean percentage change at Week 52 from parent study Baseline in bone mineral density lumbar spine (L1-L4) will be compared with a pre-specified clinically acceptable threshold of -2.2% to evaluate magnitude of bone mineral density loss after 52 weeks of treatment. If the lower bound is > -2.2%, the bone mineral density loss for the relugolix add-back treatment will be considered insignificant. As supportive analysis, least square means and 95% CI for % change at Week 52 from parent study Baseline in bone mineral density will be provided based on mixed effects model (assumed missing at random) for each parent study treatment group.

All data will be listed and summarized by visit. The change, percent change from parent study Baseline to Weeks 36 and 52 and associated 95% CIs will be presented by the parent study treatment group for each bone mineral density parameter. The number and percentage of patients meeting a bone mineral density decline of at least 4%, 5%, 6%, or 7% by body area (lumbar spine, total hip, or femoral neck) will be estimated with 95% CIs by the parent study treatment group.

Additional analyses will be performed to exam the correlation between bone mineral density loss with demographic and baseline characteristics and with treatment exposure. Details will be provided in the SAP.

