9.3.4. Bone Mineral Density

Corrected BMD data will be used for analysis as determined by the central radiology laboratory in the three prespecified anatomical locations: lumbar spine (L1–L4), total hip, and femoral neck.

BMD measured at Baseline, Week 12, Week 24, Week 36, and Week 52 visits will be summarized descriptively by parent study treatment group and each measured anatomical location for all patients in the Extension Safety population. Percentage changes from baseline along with 95% CIs of mean percentage changes also will be summarized by parent study treatment group and anatomical location. Mean percentage change from baseline with its corresponding 95% CI will be plotted by visit, parent study treatment group, and anatomical location.

A mixed-effects model with repeated measures will be used to assess BMD at 12, 24, 36, and 52 weeks. The model will be generated separately for each parent study treatment group and will have age at Baseline, visit, Baseline BMD value, stratification factors (geographic region and menstrual blood loss volume [as entered in the interactive web response system at the time of randomization]), race (African American versus Other), and BMI at Baseline as fixed effects using an unstructured variance-covariance matrix. Least square means on each anatomical location will be presented and plotted at each visit with associated 95% CIs. Categorical representation of percentage change from Baseline to 12, 24, 36, and 52 weeks of treatment will be presented by the number and proportion of patients who had BMD declines of $\leq 2\%$, $>2\%$ to 3% , $>3\%$ to 5% , $>5\%$ to 8% , and $>8\%$ by parent study treatment group and anatomical location. The 95% CIs will be provided for the respective proportions.

Categorical changes from Baseline in overall BMD (defined as lumbar spine and total hip) also will be assessed at 12, 24, 36, and 52 weeks. Femoral neck evaluates a smaller area of bone mass than the total hip and is prone to lower precision in the measurement (Leslie 2007; ISCD Official Positions 2015). Since femoral neck BMD may be associated with discordant readings compared with the total hip or lumbar spine due to technical considerations, it is not expected to add meaningful interpretation of overall BMD changes in response to treatment, though will be included for completeness.

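### Excluding a mean bone loss of 2.2% or more is not the same as preventing bone loss, and the SAP neither carries the -2.2% rule nor says it was dropped

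*Protocol*

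**What the plan says.** The Protocol synopsis (Section 1, statistical methods for safety) takes Group A women who enrolled in the extension. It compares the lower bound of the 95% CI for their mean lumbar spine (L1-L4) percentage change at Week 52 with a "pre-specified clinically acceptable threshold of -2.2% to evaluate magnitude of bone mineral density loss after 52 weeks of treatment". The conclusion attached to a pass is: "If the lower bound is > -2.2%, the relugolix add-back treatment arm will be considered to have successfully prevented bone mineral density loss".

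Protocol 9.5 applies the same bound to the arithmetic mean but words the conclusion differently: "the bone mineral density loss for the relugolix add-back treatment will be considered insignificant". It then adds a mixed-model result: "As supportive analysis, least square means and 95% CI for % change at Week 52 from parent study Baseline".

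On purpose, Protocol 4.2 says the regimen is given "to prevent the bone mineral density loss and ameliorate some of the other side effects of a hypoestrogenic state", and Protocol 7.10 says add-back "will be evaluated for maintenance of bone mineral density during treatment with relugolix".

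SAP 9.3.4 plans the estimates: "Percentage changes from baseline along with 95% CIs of mean percentage changes also will be summarized by parent study treatment group and anatomical location". It also plans a repeated-measures model for each group, categories of decline, Z-scores and subgroups. The figure -2.2% and the lower-bound comparison appear nowhere in the SAP. SAP 2.2 says in general terms that no formal testing is planned, without naming this rule.

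**The concern.** A margin of acceptable loss tolerates some loss by construction, so clearing it cannot show that loss was prevented. As a test of size against a margin the rule is sound; the conclusion goes further than the test does. A reader will take it as answering the aim in Protocol 4.2 and the maintenance question in 7.10, and the rule tests neither.

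Two further problems compound this. One result carries two pre-specified conclusions: the synopsis says the loss was prevented, while 9.5 presupposes a loss and calls it insignificant. That word may mean clinically insignificant, but beside a confidence interval it can be read as statistically non-significant. In addition, the SAP is silent, so nobody can tell whether the rule will be reported. SAP 4.2, by contrast, openly declares its departures from the protocol on analysis populations.

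This is the only study-level decision rule for the bone safety endpoint. The report could state that bone loss was prevented next to an interval that shows a mean loss.

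**Working it through.** **Nothing to reproduce.** The -2.2% comes with no derivation, SD, power or sample size. The only stated size is the whole study: 75% of 780 = 585, given as approximately 600 (Protocol 9.3).

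**What a pass establishes.** SAP 4.1 makes confidence intervals two-sided, so requiring the lower 95% bound to exceed -2.2% rejects a mean change of -2.2% or worse at one-sided 0.025. It says nothing about zero.

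**When a pass coincides with a demonstrated loss.** Let m be the observed mean and h the half-width, h = t(0.975, n-1) × SD / √n.

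- The rule passes when m - h > -2.2, that is, m > -2.2 + h.
- The whole interval lies below zero when m + h < 0, that is, m < -h.
- Both hold for -2.2 + h < m < -h, a range that exists whenever h < 1.1.

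This needs no assumption about the data. Assumptions enter only in judging how likely h < 1.1 is.

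**Assumed inputs (illustration only).**

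- n = 200: one third of 600, if the parent groups contribute equally.
- n = 150: 200 × 0.75, if a quarter have no Week 52 scan. Protocol 6.3 makes missing scans possible ("for patients whose last dose of study drug is during Week 32 or earlier, the following procedures do not need to be performed", with bone densitometry on that list) but gives no rate.
- n = 100: the number of Group A Week 52 completers that triggers the interim safety analysis in SAP 3.1, used as a pessimistic case.
- SD of percentage change: 3 and 5 points.

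| n | SD | h | Means that pass with CI wholly below zero | 95% CI at an observed mean of -1.1% |
|---|---|---|---|---|
| 200 | 3 | 0.418 | -1.78 to -0.42 | -1.52 to -0.68 |
| 200 | 5 | 0.697 | -1.50 to -0.70 | -1.80 to -0.40 |
| 150 | 3 | 0.484 | -1.72 to -0.48 | -1.58 to -0.62 |
| 150 | 5 | 0.807 | -1.39 to -0.81 | -1.91 to -0.29 |
| 100 | 3 | 0.595 | -1.60 to -0.60 | -1.70 to -0.50 |
| 100 | 5 | 0.992 | -1.21 to -0.99 | -2.09 to -0.11 |

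Every interval in the last column passes the rule and excludes zero. With n = 200 and SD 4 (h = 0.558), the lowest passing mean is about -1.64%, with an interval of about -2.20% to -1.08%.

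**SD at which the conflict vanishes.** Setting h = 1.1 gives SD = 1.1 × √n / t: 7.89 for n = 200, 6.82 for n = 150 and 5.54 for n = 100.

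**How often.** If the true mean loss is 1.0%, the probability of passing with the interval wholly below zero (normal approximation, SD treated as known) is 0.997 (n = 200, SD 3), 0.73 (n = 200, SD 5), 0.89 (n = 100, SD 3) and 0.17 (n = 100, SD 5).

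**The case against.** The best defence is that the synopsis puts the margin before the label, so prevented is an operational definition meaning no loss beyond the acceptable threshold. The formal safety objective concerns changes in bone mineral density and sets no zero-loss hypothesis; 4.2 and 7.10 are rationale. Protocol 9.5, the detailed section, accepts that some loss may exist. This softens the point but does not remove it. The conclusion will be quoted without its definition, and the two sections still state different conclusions for one result.

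A second objection is that the mean, its interval and the model-based estimates will be tabulated and plotted, so anyone can see whether zero is excluded. That stands, and it limits the harm to the stated conclusion.

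Third, if the SAP governs reporting and omits the rule, the label may never be issued. That is possible, but the protocol rule remains in force and the SAP does not say it was dropped. Silence leaves both outcomes open.

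Fourth, the SD and Group A sizes are assumed, and at n = 100 the SD limit of about 5.5 is close to the top of the assumed range. That is correct, and at n = 100 with SD 5 the overlap is narrow. The logic does not depend on these inputs.

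Finally, rewording the protocol is an amendment needing ethics committee approval. That is a real cost and bears on where to make the change.

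**Conclusion.** The concern holds and should be fixed. The pre-specified conclusion in the synopsis does not follow from its rule: a pass excludes a mean loss of 2.2% or more and nothing else. It can occur with an interval wholly below zero whenever the half-width is under 1.1 points. Under the assumed 150 to 200 women and SD of 3 to 5, the affected observed means run from -1.78% to -0.42% at the widest (n = 200, SD 3) and from -1.39% to -0.81% at the narrowest (n = 150, SD 5). The second label in Protocol 9.5 and the undeclared omission from SAP 9.3.4 are matters of text and rest on no assumption. The -2.2% margin is not challenged.

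**What to change.** In Protocol Sections 1 and 9.5, replace both labels with one statement: *a mean loss of 2.2% or more is excluded*. Report the 95% CI beside it and note whether it excludes zero.

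In SAP 9.3.4, add: *For Group A, lumbar spine (L1-L4), at the final analysis, the lower bound of the 95% CI for the arithmetic mean percentage change from parent study Baseline to Week 52 is compared with -2.2%. If it is above, a mean loss of 2.2% or more is excluded. The mixed-model LS mean with its 95% CI is supportive.* Naming the final analysis is an addition to Protocol 9.5, suggested because SAP 3.1 also plans an interim safety analysis. If the sponsor means to drop the rule, the SAP should say so and why.

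No new data or model is needed. The protocol rewording requires ethics committee submission (Protocol 10.1.2 and 10.2.1). If that is judged disproportionate, the SAP text alone can settle the reported conclusion, since SAP Section 1 allows changes until it is finalised before database lock. The remaining downside is a less favourable-sounding conclusion.

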1.1. Schedule of Activities

Table 1: Schedule of Activities for Study MVT-601-3003

PERIOD	OPEN-LABEL TREATMENT									SAFETY FOLLOW-UP
	VISIT NAME (Timing is relative to MVT-601-3001/-3002)	Week 24/Baseline (Week 24 of Parent Study; Baseline of Extension Study)	Week 28	Week 32	Week 36	Week 40	Week 44	Week 48	Week 52 ^a (or Early Termination of Study Drug)	
Visit Window (days)	Parent Study Day 169 - 10 to + 20	± 7	± 7	± 7	± 7	± 7	± 7	± 10	-	- 3 to + 18
Informed Consent	X ^d									
Review Eligibility Criteria	X									
Concomitant Medications ^e	X ^f	X	X	X	X	X	X	X	X	X
Vital Signs (BP, HR, Temperature)	X ^g	X	X	X	X	X	X	X	X ^h	X
Weight	X ^g			X				X	X ^h	
Complete Physical Examination	X ^g							X		
Visual Acuity ⁱ	X ^g									
Signs and Symptoms-Directed Physical Examination ⁱ		X	X	X	X	X	X		X ^h	X
12-Lead ECG ^k	X ^g							X	X ^h	
Clinical Laboratory Tests ^l	X ^{g,m}	X	X	X	X	X	X	X ^m	X ^h	X
Pharmacodynamics Sample ⁿ	X ^{g,m}							X ^m	X ^{h,m}	
Urinalysis	X ^g							X	X ^h	
Pregnancy Test (Urine)	X ^g	X	X	X	X	X	X	X	X ^h	X

PERIOD	OPEN-LABEL TREATMENT									SAFETY FOLLOW-UP
VISIT NAME (Timing is relative to MVT-601-3001/-3002)	Week 24/Baseline (Week 24 of Parent Study; Baseline of Extension Study)	Week 28	Week 32	Week 36	Week 40	Week 44	Week 48	Week 52 ^a (or Early Termination of Study Drug)	Un-scheduled ^b	Follow-Up ^c (~30 days after last dose of study drug)
Visit Window (days)	Parent Study Day 169 - 10 to + 20	± 7	± 7	± 7	± 7	± 7	± 7	± 10	-	- 3 to + 18
Transvaginal Ultrasound ^o	X ^g							X ^p	X ^h	
Bone Densitometry ^d	X ^g			X				X ^{p,r}	X ^h	
Endometrial Biopsy	X ^{g,s}							X ^p	X ^h	
Dispense Study Treatment	X	X	X	X	X	X	X		X ^h	
Patient Paper Diary ^t	X	X	X	X	X	X	X	X	X	
Dispense Feminine Products	X	X	X	X	X	X	X		X ^h	
Feminine Product Collection and Venous Blood Sample ^u	X ^g	X	X	X	X	X	X	X	X ^h	
Treatment Compliance		X	X	X	X	X	X	X	X ^h	
Take Study Drug Dose in Clinic ^v	X ^w							X	X ^h	
Daily Self-Administration of Study Treatment ^v		X								
MIQ ^x	X ^g	X	X	X	X	X	X	X	X ^h	X
UFS-QoL Questionnaire ^x	X ^g			X				X	X ^h	
EQ-5D-5L Questionnaire ^x	X ^g							X	X ^h	
Adverse Event Collection ^y	X ^z	X	X	X	X	X	X	X	X	X
Status of Menstruation Recovery										X ^{aa}

BP, blood pressure; ECG, electrocardiogram; EQ-5D-5L, European Quality of Life Five-Dimension Five-Level Scale; HR, heart rate; MIQ, Menorrhagia Impact Questionnaire; UFS-QoL, Uterine Fibroid Symptom and Health-Related Quality of Life

- ^a The week 52 visit must occur on or after the 1-year anniversary of Study Day 1 in the parent study. The timing of the visit should also be at least 28 weeks (± 10 days) from the actual date of the Week 24/Baseline visit.
- ^b Unscheduled visits may be conducted at the investigator's discretion when needed. The reason for the visit will be captured in the source documents.
- ^c The Follow-up visit may be waived if the patient enrolls directly into another relugolix clinical study upon completion of the Week 52 visit.
- ^d May be signed up to 30 days prior to the Week 24/Baseline visit or during the Week 24/Baseline visit. Enrollment in MVT-601-3003 is defined by administration of the first dose of MVT-601-3003 study drug.
- ^e Record all prescription and nonprescription drug and supplements taken from the Week 24/Baseline visit through the Safety Follow-Up period. Concomitant medications with start date prior to the first dose of study drug for MVT-601-3003 should be reported as concomitant medications in the parent study (MVT-601-3001 or MVT-601-3002). Concomitant medications initiated during the MVT-601-3001 or MVT-601-3002 studies and ongoing at the time of the first dose in Study MVT-601-3003 will be recorded in the electronic case report form.
- ^f Concomitant medications are recorded both for the parent study and for MVT-601-3003 at the Week 24/Baseline visit. (See footnote c for further details).
- ^g This is a parent study (MVT-601-3001 or MVT-601-3002) Week 24 procedure that serves as the Week 24/Baseline procedure for MVT-601-3003 and is covered under the informed consent for the parent study.
- ^h The indicated procedure may be performed at the Unscheduled visit based on the purpose of the visit (eg, follow-up for an adverse event or abnormal laboratory test).
- ⁱ See parent study protocols (MVT-601-3001 or MVT-601-3002) for instructions on testing visual acuity.
- ^j The exam may include a gynecologic examination, if indicated based on signs and symptoms.
- ^k The 12-lead ECGs will be submitted for central reading.
- ^l Clinical laboratory tests at each visit include clinical chemistries and a complete blood count. At the Week 24/Baseline visit and Week 52 visit, additional tests include: fasting (at least 8 hours) glucose, lipid profile, and hemoglobin A1c.
- ^m Samples should be obtained in a fasted state (at least 8 hours). Water is allowed during the fasting period.
- ⁿ Pharmacodynamic samples: For Week 24/Baseline samples, see the parent protocol (MVT-601-3001 or MVT-601-3002). At Week 52/Early Termination, collect samples for analysis of estradiol concentrations only. On days when pharmacodynamic samples are collected, administer the study treatment after the pharmacodynamic sample collections are completed.
- ^o Transvaginal ultrasound, with or without transabdominal ultrasound and with or without saline or gel contrast, is performed to determine uterine and myoma volumes and endometrial thickness and to exclude any other uterine or pelvic pathology. To avoid inter-observer and inter-device variations, a single operator will be assigned to a patient and will perform each of the ultrasound scans using the same device as far as possible. Note: Transvaginal ultrasound is required. Once the transvaginal ultrasound is done, a transabdominal ultrasound may also be done if the uterus cannot be adequately imaged on transvaginal ultrasound; for example, due to enlarged size. Results must be submitted to a central reader.
- ^p This procedure is not required at the Early Termination visit in patients whose last dose of study drug was taken during Week 32 or earlier. However, the procedure may be done if it will aid in the evaluation of an ongoing adverse event.
- ^q Bone densitometry (L1-L4, total hip, femoral neck) will be submitted for central reading.
- ^r At the Week 52 visit or at an Early Termination visit occurring on or after Week 36, patients with a bone mineral density loss of > 3 relative to the parent study Baseline measurement will undergo a follow-up bone densitometry scan at 6 (± 1) months and will be contacted to question them about medications and conditions (eg, pregnancy) that might affect bone mineral density through the time of follow-up bone densitometry. If Early Termination occurs prior to Week 36, follow-up bone densitometry will be performed according to the requirements of the parent study. The follow-up bone densitometry will be submitted for central reading.

-
- ^s Endometrial biopsies are to be performed per instructions in the parent study. See the Laboratory Manual for guidance on handling and shipping the biopsy sample to the central laboratory for analysis. An endometrial biopsy will have been performed at the parent study Week 24 visit for all patients who participated in MVT-601-3001 (see MVT-601-3001 protocol for details) and in some patients who participated in MVT-601-3002 (see MVT-601-3002 protocol for details).
- ^t Patients enter diary information on menstruation status and feminine product use daily starting on the day of the Week 24/Baseline Visit.
- ^u A venous blood sample (for hemoglobin) must be collected each time feminine products are collected to be sent to the central laboratory conducting the alkaline hematin assessment. The site must document the start and stop dates of the patient's menses corresponding to the collected feminine products.
- ^v Patients will take the first dose of the study drug for this study once daily starting with the Week 24/Baseline visit (taken at the visit). The first dose of study drug for this extension study must not be taken until all parent study Week 24 procedures such as laboratory tests have been completed. The last dose of study drug will be taken in the clinic during the Week 52/Early Termination visit.
- ^w Pregnancy test must be negative before the study drug dose is administered.
- ^x The patient will enter her response(s) into an electronic tablet device at the site.
- ^y Collect adverse events from the time that the first dose of study drug for MVT-601-3003 is administered. Adverse events with onset prior to the first dose of study drug for MVT-601-3003 should be reported as an adverse event in the parent study (MVT-601-3001 or MVT-601-3002). If events originating in the parent study are ongoing at the time of the first dose of study drug for MVT-601-3003, please see the Study Reference Manual for instructions for recording the follow-up status.
- ^z Adverse events are collected for both the parent study and for MVT-601-3003 at the Week 24/Baseline visit (see footnote v for further details).
- ^{aa} Patients whose menses have not resumed as of the Follow-up visit for whom there is no explanation for the lack of resumption (eg, medical procedure or medications) will be contacted again by telephone 3 (+0.5) months after the Follow-Up visit to determine if menses has resumed and questioned about factors that may affect resumption of menses.

